7.2.4 TIME PERIOD AND FREQUENCY FOR EVENT ASSESSMENT AND FOLLOW-UP

The occurrence of an adverse event (AE) or serious adverse event (SAE) may come to the attention of study personnel during study visits and interviews of a study participant presenting for medical care, or upon review by a study monitor. Study staff will immediately notify the principal investigator ([name]) upon becoming aware of deaths occurring in study participants. The PI will report deaths to the NIA PO within 48 hours by email and submitting the appropriate case report form (CRF).

Deaths and same-hospital readmissions (inpatient, observation, or emergency department visits) occurring within 90-days of hospital discharge will be collected retrospectively from the patient's medical record every six months through the study. All AEs/SAEs will be reported in a semi-annual summary safety report to the Data Safety Monitoring Board (see Section 9.1.4).

All AEs including local and systemic reactions not meeting the criteria for SAEs will be captured on the appropriate CRF. Information to be collected includes event description, time of onset, clinician's assessment of severity, relationship to study product (assessed only by those with the training and authority to make a diagnosis), and time of resolution/stabilization of the event. All AEs occurring while on study must be documented appropriately regardless of relationship. All AEs will be followed to adequate resolution.

Any medical condition that is present at the time that the participant is screened will be considered as baseline and not reported as an AE. However, if the study participant's condition deteriorates at any time during the study, it will be recorded as an AE.

Changes in the severity of an AE will be documented to allow an assessment of the duration of the event at each level of severity to be performed. AEs characterized as intermittent require documentation of onset and duration of each episode.

8 STATISTICAL CONSIDERATIONS

8.1 STATISTICAL HYPOTHESES

Hypothesis 1: PHARM-DC will reduce post-discharge utilization reduction of 2.5% (% of patients with readmissions or ED visits within 30 days of hospital discharge) from a baseline of 27.5%.

8.2 SAMPLE SIZE DETERMINATION

We will use a two-sided likelihood ratio test to compare the proportion of patients with utilization within 30 days of discharge between the intervention and usual care groups. Assuming 80% power and a type I error rate of 0.05, a two-sided Z test between two proportions with **4,888 subjects per group** would detect a difference of at least 2.49% from a baseline of 27.5%. Thus, our primary statistical analysis will be a two-sided Z test. We will also compare the baseline characteristics of those subjects across both arms to ensure there are no major differences. All enrolled patients will be analyzed.

Table 5 shows that varying the baseline utilization proportion does not substantially alter the minimum detectable difference. We also performed a sensitivity analysis assuming that 7.5% of patients in the intervention arm were unreachable or refused a phone call. Even at this rate, which is our best estimate from our pilot data, we would have 80% power to detect a difference of 2.54%. Finally, these rates were robust to contamination rates of 2% among patients in the usual care arm. We believe this low rate is a reasonable estimate for contamination, because patients thought to have a clear need for these services will be excluded from the RCT, and because we believe that non-pharmacist clinicians will remain so busy that they will not begin to provide such services to other patients.

Table 5. How Baseline Utilization Affects Minimum Detectable Difference

Percentage of Patients with Utilization within 30 Days of Hospital Discharge		
Usual Care	Intervention	Minimum detectable difference
30.0%	27.44%	2.56%
27.5%	25.01%	2.49%
25.0%	22.59%	2.41%

For the qualitative study, the study will enroll up to 48 people in the focus groups, 15 people in the Year 2 interviews, and 50 people in the interviews per site.

8.3 POPULATIONS FOR ANALYSES

We will conduct the following analyses:

- Intention-to-Treat (ITT) Analysis Dataset (i.e., all randomized participants)
- Modified Intention-to-Treat Analysis Dataset (e.g., participants who had the in-hospital intervention but did not respond to post-discharge phone calls)
- Per-Protocol Analysis Dataset: defines a subset of the participants in the full analysis (ITT) set who complied with the protocol sufficiently to ensure that these data would be likely to represent the effects of study intervention according to the underlying scientific model (e.g. participants who had both the in-hospital intervention and the post-discharge phone call).

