Description of Sites/Facilities Enrolling Participants: Two sites will participate in this study: an academic medical center (Brigham and Women's Hospital in Boston, Massachusetts) and a university-affiliated community hospital (Cedars-Sinai Medical Center in Los Angeles, California ¹) that has some community physicians.

Description of Study Intervention: *Pharmacist-led Hospital Discharge Care Intervention:*
Eligible pharmacists (those with training in transitions of care) at the two sites will receive a list of patients currently admitted to the hospital who meet the inclusion/exclusion criteria. Eligible patients will meet with a clinical pharmacist for medication reconciliation.

Clinical pharmacists will conduct an initial medication regimen assessment, which will use tools in the PHARM-DC Toolkit to identify potentially inappropriate medications. Patients and/or their caregivers will undergo a pre-discharge intervention, where clinical pharmacists will anticipated discharge medication changes.

The Toolkit content and 1-2 hours of introductory training add three major components:

1. Pharmacists will use the *PHARM-DC Toolkit*, which *summarizes the evidence* for post-discharge medication management. The Toolkit includes a (1) the Start Actions for Assessing Adherence Barriers worksheet, integrated into an Epic template, (2) the Beers Medication List, (3) Pre-Discharge Worksheet, integrated into an Epic template, (4) Up-to-Date

Section on prescribing to older adults, (5) Discharge Worksheet, integrated into an Epic template, (6) Post-Discharge Worksheet, integrated into an Epic template.

2. Pharmacists will assess patient needs and customize accordingly. All patients will receive one discharge counseling visit and one post-discharge phone call, but pharmacists will find that some patients need further phone calls, interventions, referrals, or other interactions.

During training, trainers will emphasize to pharmacists participating in this study additional, clinically-indicated services may be provided to control group patients to ensure that it is clear that routine services that are part of the PHARM-DC and that the toolkit should not be withheld from the control group if they are clinically indicated.

Study Duration: 36 months

Participant Duration: Participation during one hospital admission/discharge

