 - i. Will receive usual care, which may include pharmacist consultation and/or after-discharge phone call(s) if clinically necessary.
- g. Critical covariates, including, age, sex, gender, all recorded diagnoses, number of medications, all recorded medication types, zip code, first language, marital status, employment, social history (e.g. tobacco use, alcohol use) will be extracted from electronic health records (EHR) after the intervention ends at each study site. The complete list of data elements to be extracted from the EHR for evaluating trial outcomes are provided in **Appendix A**.

(2) Qualitative study to study barriers and facilitators of implementing PHARM-DC:

- a. In the first year of the intervention, the investigators ([name] and [name]) will visit trial sites to conduct 6 focus groups of 6 to 8 clinicians. These focus groups will be grouped by type of clinician (pharmacist, pharmacy tech, physician, nurse). We estimate that 48 people per site will participate in the study.
- b. We will use a purposive sampling design by role and department to determine eligibility.
- c. Eligible participants will receive an email from study staff inviting them to participate in the focus groups.
 - i. Documents:
 1. Recruitment email
 2. Information sheet
- d. Focus groups will be 60-90 minutes and will be administered by the PI, the qualitative researcher, and study staff. Due to COVID-19, the focus groups may take place virtually using video conferencing software (e.g. Webex).
- e. We may also conduct phone or video interviews in lieu of focus groups if individuals are not available for the focus groups.

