3 OBJECTIVES AND ENDPOINTS

Primary Outcome

We chose an endpoint of 30-day post-discharge utilization as our primary outcome because the RE-AIM model points to the importance of institutional-level effectiveness and cost. We chose to power this trial on an absolute utilization reduction of 2.5% (% of patients with readmissions or ED visits within 30 days of hospital discharge) from a baseline of 27.5%.

We define this utilization in two different ways, based on what data is available. For the first analysis, we will use same-hospital utilization data. Both site PIs can electronically access inpatient admission, observation stay, and ED visit data for their health system. These three utilization types will represent the basis for the first RCT analysis (*manuscript #2 above*).

We recognize the limitations of same-hospital utilization data.^{xxx} As such, the RCT is powered on a primary endpoint of same-state 30-day hospital readmissions and ED visits (manuscript #6 above).

This utilization will be tracked with data from the Massachusetts All Payer Claims Data (APCD) database and California's Office of Statewide Health Planning and Development.^{xxxi} Because we expect little utilization in other states (discharge to another state is an exclusion criterion) and because we do not anticipate any differential effect on such utilization, we will not track it. Statewide data sources do not track observation stays, so they will be excluded from statewide analyses. However, we will conduct a sensitivity analysis projecting changes in same-hospital observation stays to the statewide analysis.

The current version of this protocol does not include information for these analyses using other data sources; we will include this information in subsequent versions through protocol/IRB amendments.

Secondary Outcomes

We will examine the endpoints in the following subgroups:

Patients:

- 1) Patient socioeconomic status (estimated via median income of home census tract);
- 2) Patient medication adherence and literacy (as assessed by study pharmacists, in addition to using limited English proficiency as a proxy for low medication literacy);
- 3) Study site;
- 4) Ten or more medications;
- 5) Three or more high risk medications;
- 6) Patient history of congestive heart failure;
- 7) By receipt of different intervention components;
- 8) Patient age groups;
- 9) Before and after historical changes to the intervention and control arms;

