6 STUDY INTERVENTION

6.1 STUDY INTERVENTION(S) ADMINISTRATION

6.1.1 STUDY INTERVENTION DESCRIPTION

PHARM-DC Intervention Overview

Pharmacists at both study sites have experience in providing discharge counseling and in making post-discharge phone calls. This experience will ensure that PHARM-DC is being tested in its best light. The Toolkit content and 1-2 hours of introductory training add three major components:

1. Rather than incorporating content based solely upon their prior training and experience, pharmacists will use the *PHARM-DC Toolkit*, which *summarizes the evidence* for post-discharge medication management.
2. Pharmacists will *assess patient needs* and *customize accordingly*. All patients will receive one discharge counseling visit and one post-discharge phone call, but pharmacists will find that some patients need further phone calls, interventions, referrals, or other interactions.
3. Although pharmacists have long been successful in leading med rec interventions, most work focused on *what medications patients had been prescribed and are taking*. This is a necessary step, but we believe most benefit occurs from the subsequent step of figuring out what medications patients *should be taking*.

PHARM-DC toolkit:

- 1) Pharmacist review of discharge med rec and medication appropriateness (e.g., reduction in polypharmacy);
- 2) In-hospital room visit to screen for previous barriers to safe medication use, initiate management of these barriers, and communicate with post-discharge providers regarding likely actions that will need to be taken;
- 3) Post-discharge phone call by a pharmacist 1-3 days after discharge to screen for patient/caregiver lack of understanding of their medication regimen, medication non-adherence, early side-effects, lack of knowledge of what ADEs to watch for and what to do if they occur, other barriers to safe medication use, and management of these problems;

4) Based on this risk assessment, pharmacists will tailor the interventions to each patient. The personalized intervention may include:

- a. **Patient education, counseling, and coaching** regarding the importance of taking medication as prescribed and contacting a designated caregiver or provider if there are problems;
- b. **Taking further steps to improve medication appropriateness;**

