8.4 STATISTICAL ANALYSES

8.4.1 GENERAL APPROACH

- We will use chi-square tests, Analysis of Variance (ANOVAs), logistic regression, and means/medians for descriptive statistics.
- We will use a 0.05 cutoff for p-values and 95% confidence intervals for statistical significance.

- Our primary statistical analysis will be a two-sided Z test. We will also compare the baseline characteristics of those subjects across both arms to ensure there are no major differences. All enrolled patients will be analyzed.
- We will check for normality and log-transform variables if necessary for skewed distributions.
- We will calculate all-cause unplanned post-discharge utilization within a 30-day period from the date of discharge from an index admission. Post-discharge utilization will include emergency department visits, observation stays, and inpatient readmissions. Planned readmissions will be excluded using the Centers for Medicare and Medicaid's Planned Readmissions Algorithm. The algorithm assesses a dichotomous yes or no outcome of whether each admitted patient has any unplanned readmission within 30 days. In accordance with the CMS algorithm, if a patient has more than one unplanned admission within 30 days of discharge from the index admission, only the first is considered a readmission. If the first readmission after discharge is planned, any subsequent unplanned readmission is not considered in the outcome for that index admission because the unplanned readmission could be related to care provided during the intervening planned readmission rather than during the index admission.

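### The per-protocol example in section 8.3 depends on a call made after the outcome clock starts and has no rule for controls; comparing call-completers with all controls would build in a bias from early returns

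*Combined protocol and SAP*

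**What the plan says.** Section 8.3 commits to three analysis sets: all randomised participants, a modified ITT set and a per-protocol set. The per-protocol set is described in general terms as the part of the ITT set that adhered well enough for its data to reflect what the intervention does. Its one illustration is "participants who had both the in-hospital intervention and the post-discharge phone call". The modified ITT set is illustrated by "participants who had the in-hospital intervention but did not respond to post-discharge phone calls".

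The call is a study-arm component in sections 1.3 and 6.1.1: "Post-discharge phone call by a pharmacist 1-3 days after discharge". Control patients receive usual care, "which may include pharmacist consultation and/or after-discharge phone call(s) if clinically necessary" (section 1.3).

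The outcome is counted "within a 30-day period from the date of discharge from an index admission", and "Post-discharge utilization will include emergency department visits, observation stays, and inpatient readmissions" (section 8.4.1). Sections 8.2 and 8.4.1 say that every enrolled patient is analysed and that the primary test is a two-sided Z test. Section 3 adds a subgroup analysis "By receipt of different intervention components".

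The plan does not say which controls belong to the per-protocol or modified ITT set. It does not say how to classify a patient who returns before the call, and it gives no landmark or adjustment for these comparisons.

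**The concern.** Membership of the per-protocol set, as illustrated, depends on something that happens after follow-up has begun. A patient readmitted on day 1 or 2 may never get the call, and so leaves the set because of the outcome being measured. A comparable control has no scheduled call to miss. If all controls are kept, early events are removed from one arm only, and a benefit can appear where none exists.

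Section 8.3 presents this set as informative about the intervention's effect, so the result could be read beside a small or null ITT difference. Because the adherence standard is not defined for controls, their rule could also be settled after results are known. The modified ITT example has the same gap, and so does the component subgroup if the call is one of the components.

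**Working it through.** **1. The plan's own figures (section 8.2).** Inputs: 27.5% against 25.01%, two-sided alpha 0.05, 80% power, 4,888 per group.

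Pooled Z test: n = [1.960 × √(2 × 0.26255 × 0.73745) + 0.842 × √(0.275 × 0.725 + 0.2501 × 0.7499)]² / 0.0249² ≈ 4,901. This agrees with 4,888, for which power is 79.9% and the detectable difference is 2.49 points.

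Section 8.2 also gives 2.54 points when 7.5% of the intervention arm is unreachable or refuses the call. Three ways to obtain such a figure:

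- remove 7.5% from the intervention arm only (4,521 against 4,888): 2.54
- remove 7.5% from both arms: 2.59
- dilute the effect, 2.49/0.925: about 2.70

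Only the one-arm removal matches. That is consistent with keeping all controls, but it does not prove that the per-protocol set will be built that way.

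**2. Early-return component, all controls kept, no true effect.** Let p = 0.275. Let f be the share of 30-day events that occur before the call, and m the share of those events that prevent it. The documents give neither f nor m. Assume events spread evenly over 30 days and a day-3 call, so f = 3/30 = 0.10. The fraction of the arm removed is x = p × f × m, and the remaining intervention rate is (p − x)/(1 − x). The last column uses the pooled Z test with 4,888 × (1 − x) against 4,888; the nominal value is 2.5%.

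| m (assumed) | x | Intervention rate | False benefit (points) | Chance of a significant false benefit |
|---|---|---|---|---|
| 10% | 0.275% | 27.30% | 0.20 | 4.1% |
| 25% | 0.69% | 27.00% | 0.50 | 8.0% |
| 50% | 1.375% | 26.49% | 1.01 | 20.1% |
| 100% | 2.75% | 25.45% | 2.05 | 62.6% |

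Example at 50%: (0.275 − 0.01375)/(1 − 0.01375) = 0.2649, and 27.50 − 26.49 = 1.01.

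The last row is the ceiling for even spread and a day-3 call. A day-1 call (f = 1/30) gives 0.33 at m = 50% and 0.67 at 100%. Events concentrated soon after discharge would raise the figures: f = 0.15 with m = 50% gives 1.53.

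**3. Selection on not answering.** Take the 7.5% from section 8.2 and an assumed risk ratio RR for non-answerers against answerers. The rate in answerers is 0.275/(0.925 + 0.075 × RR).

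- RR 0.75: 28.03%, 0.53 points toward harm
- RR 1.25: 26.99%, 0.51 toward benefit
- RR 1.5: 26.51%, 0.99 toward benefit
- RR 2: 25.58%, 1.92 toward benefit

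Steps 2 and 3 cannot simply be added if the 7.5% already includes early returners. If it does not, the two cancel at f = 10%, m = 50% when non-answerers have a 30-day rate of 0.275 − 0.01375 × 0.725/0.075 = 14.2%.

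**4. What a day-3 landmark leaves.** With 10% of events before day 3, the control rate after the landmark is 0.2475/0.9725 = 25.45%. Under no true effect, answerers who are event-free at day 3 have (0.9 × 0.28026)/(1 − 0.1 × 0.28026) = 25.95% at RR 0.75, and 24.50% at RR 1.5. The early-return component is gone, but selection on answering remains: 0.50 points toward harm or 0.94 toward benefit.

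**The case against.** The call is only an example under a general adherence definition that covers both arms. Read literally, the example would admit almost no controls, so a one-arm filter is an inference. A control who received usual care, with or without a call, could fairly be counted as adherent: the synopsis says routine services in the "toolkit should not be withheld from the control group if they are clinically indicated". All of this stands. The one-arm filter is one reading, and the certain gap is that adherence is not defined for controls.

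The size is also open to challenge. Patients treated in the ED and sent home can still be called, and the call may reach a caregiver. Section 8.2 puts all missed calls at 7.5%, and the 100% row alone would use 2.75/7.5 = 37% of that. This stands too, and the row is shown only as a ceiling.

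Section 8.4.2 already calls its analyses underpowered and hypothesis-shaping. That caution does not name the 8.3 sets, and it warns about negative results rather than false positive ones.

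A reader might go further and infer that the per-protocol result must favour the intervention. The documents do not support this, because non-answer selection can offset or reverse the early-return part. A reader might also infer from section 7.1, which labels non-answerers lost to follow-up, that they are dropped from the outcome analysis. Section 7.1 states no exclusion, the outcomes come from hospital and statewide records (section 3), and all enrolled patients are analysed.

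**Conclusion.** The point holds for a supplementary analysis and is minor to moderate. Two things need no assumption: the illustrated criterion uses a call made after the outcome clock starts, and no membership rule exists for controls. If call-completers are compared with all controls, the early-return component can only favour the intervention.

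Its size rests on assumed inputs: 0.2 to 1.0 points for 10% to 50% blocking with even event spread and a day-3 call, and 2.05 at most under that spread, against the 2.49-point target. Confidence is high for the gap, moderate for the direction of this component, and low for its size. The net sign of the whole comparison is not established. The primary ITT analysis is not affected.

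**What to change.** Put this in section 8.3:

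> Effectiveness conclusions rest on the ITT comparison. Call-completers will not be compared with all controls followed from discharge. Any call-based per-protocol analysis will start at a day-3 landmark in both arms among patients with no return visit by then, will adjust for pre-specified baseline covariates, and is exploratory. It does not capture effects in days 0 to 3, and selection on answering remains.

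State one membership rule per arm for the per-protocol and modified ITT sets. Use the same landmark for the section 3 subgroup by intervention components wherever the call is one of them.

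A complier-average effect with assignment as the instrument is an optional addition, not a replacement, since it answers a different question. It needs one exposure definition applied in both arms and a stated exclusion restriction. Its interval is wider. The ITT half-width is 1.96 × √((0.275 × 0.725 + 0.2501 × 0.7499)/4,888) = 1.74 points. With 95% uptake (assumed) and 2% receipt in controls (the contamination rate in section 8.2), it becomes about 1.744/0.93 = 1.88.

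The cost is SAP wording and a little extra analysis, with events in days 0 to 3 dropped from this secondary comparison. Enrolment, sample size and patient care do not change.
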